5 STUDY ENROLLMENT AND WITHDRAWAL

The study is planning to enroll a total of 40 subjects that will be randomly assigned to one of the two study groups. It is anticipated that a total of 200 subjects will be screened in order to meet recruitment goals.

Participants will be pre-screened in person at the Brotman Facial Pain clinic, the Oral and Maxillofacial Surgery Clinic both at the University of Maryland, School of Dentistry, Pain Medicine Clinic at the University of Maryland, School of Medicine or by telephone.

Vulnerable subjects: No specific vulnerable populations are being targeted for recruitment for this study.

5.1 Subject Inclusion Criteria

In order to be eligible to participate in this study, an individual must meet all of the following criteria:

- 1. Provide signed and dated informed consent form
- 2. Is between 18 and 65 years of age (inclusive; male or female and any race or ethnicity)
- 3. Trigeminal neuropathic pain symptoms for a minimum of 3 months prior to randomization visit, localized in any trigeminal distribution (intraoral or extraoral).
- 4. Meets diagnostic criteria for Trigeminal neuropathic pain with diagnosis based on the International classification of headache disorders ICHD-3 [44] and International classification of Orofacial Pains ICOP [8].
- Diagnosed with idiopathic trigeminal neuralgia with concomitant continuous pain per ICDH-3.
- Diagnosed with Painful posttraumatic trigeminal neuropathy or idiopathic painful trigeminal neuropathy per ICOP. May include:
 - Subjects with a history of persistent pain of idiopathic origin or after dental extractions, mandibular fracture, surgical procedure, implant procedure and root canal therapy.
- 5. Participants must have a minimum mean of average daily pain intensity score of 4/10 in where 0= no pain and 10= maximum pain imaginable on a numerical rating scale (0-10), during the 4 weeks/28 days baseline period prior randomization.

dosage throughout the study.

- 6. If taking a prescription medication daily for the management of pain (taken for at
 - throughout the study at the same dosage.7. If taking prescription medication, opioid medication or OTC medications as needed or episodically for the management of pain agrees to discontinue its use prior to

least 30 days before baseline), agrees to continue the daily use of the medication

- the Screening and Baseline Visit.

 8. If taking OTC pain medications daily agrees to continue its daily use at the same
 - If a participant is taking an over-the-counter medication daily for management of other type of pain or for prophylaxis of myocardial infarction or stroke, the participant will be encouraged to continue the same usage of that medication throughout the study.
- 9. If subjects diagnosed with migraine, are allowed only if episodic.
- 10. Agrees to not start any new prescription medication for the management of trigeminal neuropathic pain or other type of pain throughout the study.
- 11. Agrees to not modify their prescription regimen for current trigeminal neuropathic pain or other types of pain throughout the study
- 12. Agrees not to receive any injection therapy for the management of neuropathic pain or migraine (e.g. nerve blocks, SPG blocks, steroid injections, Botox) during the course of the study
- 13. Agrees not to use any neuromodulatory device for the management of neuropathic pain or migraine during the course of the study
- 14. Agrees not to undergo any surgical procedure for the management of neuropathic pain during the course of the study
- 15. Agrees to not use CBT, biofeedback or acupuncture for the management of pain during the course of the study.
- 16. Females of childbearing potential agree to use one of the following methods of contraception throughout the study: licensed hormonal method, intrauterine device, female or male condoms with contraceptive foam, abstinence, bilateral tubal ligation/occlusion, or vasectomy in partner (if postmenopausal, must not have menstruated for at least 12 consecutive months)
- 17. Willing and able to understand and comply with all study procedures and be available for the duration of the study.

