- 15. Has been treated with another investigational drug or treatment within 30 days prior to the Screening and Baseline Visit
- 16. Has commenced a new daily prescription medication for the management of pain within 30 days prior to the Screening and Baseline Visit
- 17. Currently taking opioid medication whether episodically or daily, within 30 days prior to the Screening and Baseline Visit.
- 18. Patients sensitive to Latex
- 19. If planning to become pregnant, pregnant or breastfeeding.
- 20. Anything that, in the opinion of the investigator, would place the participant at increased risk or impede the participant's full compliance with or completion of the study.

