7 STUDY SCHEDULE

7.1 Pre-Screening

Pre-screening (0-2 weeks, Day -15 to -1)

Potential participants may be contacted by telephone or in person for pre-screening; in some instances, it may also be conducted simultaneous with the Screening and Baseline Visit (Visit 0) or during a scheduled visit to the Brotman Facial Pain Clinic, Oral Surgery Clinic or Pain Medicine Clinic (School of Medicine).

After contacting potentially eligible participants and after obtaining their verbal consent we will proceed to conduct a pre-screening interview with questions designed to identify participants with a high probability of meeting inclusion criteria. This interview will be conducted by trained study staff using a standard script. For the potential participants who express interest in the study, documentation of verbal consent, the pre-screening date, and screening ID will be recorded. In addition, an in-clinic Screening and Baseline Visit (Visit 0), will be scheduled within 2 weeks from the date of the pre-screening interview.

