7.2 Screening and Baseline Visit (Visit 0, 4 weeks period)

This visit will happen with 2 weeks after pre-screening. Participants will start the baseline period that will consist of 4 weeks.

- Obtain and document consent from subject participation in the study.
- Obtain signed Health Insurance Portability and Accountability Act (HIPAA)

Authorization

- Review medical/dental history to determine eligibility based on inclusion/exclusion criteria.
- Take blood pressure and collect weight and height.
- Review medications history to determine eligibility based on inclusion/exclusion criteria.
 - Record concomitant medications and therapies
- Perform QST examination
- Perform EEG
- Collect blood for Cytokine release assay

- - Perform urine pregnancy test (in women with childbearing potential)
 - Provide instruction to complete 4 outcome measure questionnaires in paper or electronically for review next visit
 - Provide instruction to complete Daily Symptom Diaries electronically or in paper dispense forms.

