15.3 Informed Consent Process

Potential participants may be contacted by telephone or in person for pre-screening; in some instances, it may also be conducted simultaneous with the Screening and Baseline Visit (Visit 0) or during a scheduled visit to the Brotman Facial Pain Clinic, Oral Surgery Clinic or Pain Medicine Clinic. Written informed consent will be obtained at Visit 0 in where will be evaluated eligibility, obtain demographics, medical history, medication information, and perform evaluations and provide the daily symptoms diaries and questionnaires and then schedule visit 1.

Informed consent is a process that is initiated prior to the individual agreeing to participate in the study and continues throughout study participation. Extensive discussion of risks and possible benefits of study participation will be provided to subjects and their families, if applicable. A consent form describing in detail the study procedures and risks will be given to the subject. Consent forms will be approved by the sponsor (UMB) IRB, and the subject is required to read and review the document or have the document read to him or her.

The investigator or designee will explain the research study to the subject and answer any questions that may arise. The subject will sign the informed consent document prior to any study-related assessments or procedures. Participants will be given the opportunity to discuss the study with their surrogates or think about it prior to agreeing to participate. They may withdraw consent at any time throughout the course of the study. A copy of the signed informed consent document will be given to subjects for their records. The rights and welfare of the subjects will be protected by emphasizing to them that the quality of their clinical care will not be adversely affected if they decline to participate in this study.

The consent process will be documented in the clinical or research record.

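### Inclusion criterion 7 places a study-driven stop of as-needed pain medicines before signed consent, and it does not fit exclusion 17 or section 6.6.1.2

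*Combined protocol and SAP*

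**What the plan says.** All references are to the combined protocol and SAP.

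- **Section 5.1, criterion 7.** For as-needed or episodic users of prescription, opioid or over-the-counter (OTC) pain medicines, the text reads "opioid medication or OTC medications as needed or episodically for the management of pain agrees to discontinue its use prior to" and then names "the Screening and Baseline Visit" as the deadline. No minimum interval before that visit is given.
- **Section 5.2, criterion 17.** The exclusion is "Currently taking opioid medication whether episodically or daily, within 30 days prior to the Screening and Baseline Visit".
- **Section 7.1.** The first consent step is verbal: "after obtaining their verbal consent we will proceed to conduct a pre-screening interview". Visit 0 "will be scheduled within 2 weeks from the date of the pre-screening interview", and the interview may also take place on the same day as Visit 0.
- **Section 7.2.** The first task listed for Visit 0 is "Obtain and document consent from subject participation in the study".
- **Section 15.3.** "Written informed consent will be obtained at Visit 0", and "The subject will sign the informed consent document prior to any study-related assessments or procedures".
- **Section 6.6.1.2.** OTC analgesics and anti-inflammatories are limited before Baseline to no more than 2 days a week. Episodic use, up to a stated cap, is provided for between baseline and Visit 4.
- **Appendix A.** The first table puts pre-screening 0-2 weeks before Visit 0; the second puts it 0-4 weeks before.

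**The concern.** A stop in pain medication required for eligibility is a change made because of the trial. Criterion 7 dates it before the visit at which anyone signs. People in pain could alter their treatment on the strength of a telephone or clinic interview, and some would then be found ineligible. Section 9.2 records events with start dates after informed consent, so an event that began after such a stop but before signature would fall outside that recording.

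The opioid wording makes this worse. Criterion 7 reads as an invitation to qualify by stopping, while exclusion 17 applies a 30-day look-back to the same visit. If the study's own timetable never allows 30 days, someone could stop for the trial and still be turned away. The OTC wording has a similar problem: one section requires as-needed use to end, and another tolerates limited use over the same period.

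**Working it through.** The plan states no figure on this point, so there is none to reproduce. The check compares the order of events and counts days.

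**Step 1: order of consent and medication change.**

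| Event | Timing | Source |
|---|---|---|
| Verbal consent, described for the interview | Pre-screening | 7.1 |
| Stop of as-needed pain medicines | Before Visit 0 | 5.1, criterion 7 |
| Written consent | At Visit 0 | 7.2, 15.3, Appendix A |

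The stop falls between the verbal and the written consent. If the interview and Visit 0 coincide, as section 7.1 allows, there is no earlier interview at which agreement to stop could be given.

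**Step 2: opioid clause against exclusion 17.** Let *s* be the days from last opioid use to Visit 0, and *G* the days from pre-screening to Visit 0. Exclusion 17 is read here as a 30-day look-back.

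- Criterion 7 is met if use stops at any time before Visit 0, because no interval is set.
- Exclusion 17 is avoided only if *s* is at least 30.
- For someone who stops at or after pre-screening, *s* is at most *G*.
- The minimum shortfall is therefore 30 − *G*.

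| Stated window | Longest *G* (days) | 30 − *G* (days) |
|---|---|---|
| Same-day interview (7.1) | 0 | 30 |
| Within 2 weeks (7.1; first Appendix A table) | 14 | 16 |
| Day -15 in the heading of 7.1 | 15 | 15 |
| 0-4 weeks (second Appendix A table) | 28 | 2 |

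The shortfall is positive in every row, so a stop at or after pre-screening cannot clear the look-back for that Visit 0. The last column also gives the time before the interview by which use must already have ended, even when the longest gap is used. Someone who stopped 30 days or more before Visit 0 for other reasons meets both criteria.

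**Step 3: OTC clause against section 6.6.1.2.** Criterion 7 requires as-needed or episodic OTC pain medicine to be discontinued before Visit 0. Section 6.6.1.2 tolerates use on up to 2 days a week before Baseline and defines an allowed episodic level afterwards. If Baseline there means Visit 0, which its reference to the exploratory assessment suggests, the two sections give different rules for the run-up to the same visit.

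**The case against.** The strongest reply concerns the opioid clause. An eligible person must meet every inclusion and no exclusion, so exclusion 17 governs and the outcome is determinate. That stands. A reader might infer that the two criteria contradict each other and that staff could properly reach opposite decisions on the same person. The documents do not support this: someone inside the look-back is excluded whatever criterion 7 says. What remains is a clause that can lead a person to stop and still be excluded.

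On consent, the sponsor could say that criterion 7 asks only for agreement, that the pre-screening script is not reproduced and may cover more than the interview, and that a participant's own stop is not literally an assessment or procedure under section 15.3. It could add that section 5.3 describes earlier contact through records and clinic providers. These replies soften the claim to one about the intent of 15.3 rather than its letter. They do not change the order, since the text dates the stop before Visit 0 and describes no consent that covers a treatment change.

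Sections 6.6.1.1 and 6.6.1.2 also allow OTC rescue, so OTC users are not simply left without relief. That is fair, and it is also the source of the mismatch in Step 3.

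**Conclusion.** The point holds on three counts. A study-driven medication change is placed before signed consent. The opioid clause in criterion 7 does not fit exclusion 17, by between 2 and 30 days depending on the window used. Criterion 7 does not fit section 6.6.1.2 on OTC use. The day counts assume that exclusion 17 is a 30-day look-back and that the stop occurs at or after the pre-screening interview.

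Two stronger readings are not supported.

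- **Number affected.** A reader might take 200 screened less 40 randomised = 160 (160/200 = 80%) as the number who stop medication and never enter. That would require every screen failure to be an as-needed user who stopped before failing. The number of as-needed users is not given, and the interview is meant to filter out unlikely candidates first. The figure is only an arithmetic ceiling.
- **Bias in the primary endpoint.** A reader might infer that a temporary rise in pain after stopping inflates the 28-day baseline, the entry score of 4 and the 30% responder rate. The documents give no size or duration for such a rise, it would be averaged over 28 days, and it would be expected in both randomised arms. If exclusion 17 is applied, opioid use has already ended at least 30 days before Visit 0. The effect cannot be sized, and the point does not rest on it.

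**What to change.** Amend the text so that written consent precedes any change in pain medication that the study requires. Reconcile criterion 7 (5.1), exclusion 17 (5.2), 6.6.1.2, 7.1, 7.2, 15.3 and the two Appendix A tables, so that one consistent rule and one look-back apply to as-needed opioid and OTC use and one pre-screening window is stated. The amended text should also make clear how the Visit 0 measurements and the start of the 28-day diary relate to any required change. The clinical rule and its timing are for the sponsor to decide.

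The cost is amendment wording and possibly an earlier consent signature or a small scheduling delay for as-needed users. A separate consent contact, if chosen, would be one added step.

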5.2 Subject Exclusion Criteria

- 1. Participants with a history of congestive heart failure or uncontrolled diabetes.
- 2. Participants with serious hepatic, respiratory, hematologic or immunologic illnesses, an unstable cardiovascular disease, or any other severe acute or chronic medical or psychiatric condition or laboratory abnormality that may increase the risk associated with trial participation or Erenumab or may interfere with the interpretation of trial results and, in the judgment of the investigator, would make the participant inappropriate for entry into this trial.
- 3. Participants with high blood pressure, uncontrolled high blood pressure, malignant disease, chronic constipation, any malabsorption disorders such as IBSc or any other severe acute or chronic medical or psychiatric condition (major depression, schizophrenia, dementia) or laboratory finding that may increase the risk associated with trial participation with Erenumab, that in the judgement of the investigators would interfere with study assessments and/or would make the participant inappropriate for entry into this trial.
- 4. Participants with active malignancy of any type or a history a malignancy (with exception of participants with malignancy surgically removed with no evidence of recurrence within 5 years before enrollment.
- 5. Participants with evidence or a history of drug or alcohol abuse within the past 12 months or has been diagnosed with a substance abuse disorder.
- 6. Participants with dental pain (determined pain of odontogenic/periodontal origin).
- 7. Participants with significant neurological disorders.
- 8. Patients with chronic migraine with and w/o aura following the ICHD-3 criteria treated or not treated with medication
 - Without excluding headache attributed to TMD
- 9. Participants currently taking or have previously taken Erenumab or other CGRP monoclonal antibody (mAmb) or currently taking a CGRP-Receptor antagonist (gepants) for migraine prevention.
- 10. Patients with hypersensitivity to Erenumab
- 11. Participants with trigeminal neuropathic pain taken medications for the management of trigeminal neuropathic pain in where daily dosage has been modified within three weeks before baseline.

- 12. Neuroimaging showing the presence of neurovascular compression or AV malformation.13. Neuroimaging showing the presence of intracranial pathology (i.e. multiple sclerosis, tumor).
- 14. Presence of extracranial pathology in the area of pain (tumor, lesion).
- 15. Has been treated with another investigational drug or treatment within 30 days prior to the Screening and Baseline Visit
- 16. Has commenced a new daily prescription medication for the management of pain within 30 days prior to the Screening and Baseline Visit
- 17. Currently taking opioid medication whether episodically or daily, within 30 days prior to the Screening and Baseline Visit.
- 18. Patients sensitive to Latex
- 19. If planning to become pregnant, pregnant or breastfeeding.
- 20. Anything that, in the opinion of the investigator, would place the participant at increased risk or impede the participant's full compliance with or completion of the study.

5.3 Strategies for Recruitment and Retention

Participants will be recruited from direct contact with patients who have relevant diagnoses recorded in electronic health records or patient registries at the Brotman Facial Pain Clinic, the Clinic of Oral and Maxillofacial Surgery at the University of Maryland, School of Dentistry and from the Pain Clinic at the University of Maryland, School of Medicine, Department of Anesthesiology. Providers at these clinics will be made aware of the study and asked to inform their patients about the study and to provide them with study contact information. Previous study participants who gave prior permission may be contacted. Participants may be also recruited through advertisements, websites, print, and electronic media. All recruitment materials will be submitted to the IRB for review and approval prior to their use.

Participants will be contacted to be reminded of each upcoming visit by telephone, text message, email, or letter. Participants will be informed about the importance of keeping each scheduled appointment, and they will be instructed to contact the study staff as soon as possible in case they are unable to attend a scheduled appointment. Participants who miss a scheduled visit without notifying the study staff will be contacted by telephone, text message, email, or letter to encourage their continued participation in the study and to ask them to contact the study team concerning their next appointment. Unscheduled visits may occur at the investigator's discretion (Section 7.6).

Participants will be compensated for their participation in the study in an amount stated in the informed consent form. In some cases, the participant may be eligible for reimbursement of travel expenses.

5.4 Treatment Assignment Procedures

This study will be a conventional factorial design, randomized, double-blinded clinical trial with two parallel arms to evaluate efficacy of Erenumab:

 Erenumab, a monoclonal antibody medication that inhibits CGRP pathway, which is FDA-approved for the prevention of migraine. The comparison will be to placebo.

5.4.1 Randomization Procedures (if applicable)

Extensive screening procedures of potential participants to determine their eligibility based on the inclusion and exclusion criteria will be carried out prior randomization. Participants who do not meet these criteria will not be enrolled in the study.

Randomization visit will be within 7 days after Baseline Phase period has finished (4 weeks/28 days), eligibility will be further confirmed based on completion of Daily Symptom Diaries and pain intensity score. Qualified participants will be randomly assigned to one of the two arms of the study in a 1:1 ratio:

- 1) Investigational arm: Erenumab: N= 20 participants
- 2) Placebo: N=20 participants

Randomization

Subjects will be randomized to the investigational treatment group (Erenumab) or the placebo group using a blocked randomization scheme. The examiners and patients will be blind to the group assignment. Randomization will be done by Investigational Drug Services (IDS/Research pharmacy). There will be a 1:1 ratio of treatment to placebo participants.

Blinding

Blinding will be done by Investigational Drug Services (IDS). The PI and study staff will be blind to what the participant is receiving.

Treatment/randomization codes

IDS will be responsible for randomization of participant assignment to either the study medication or placebo groups. IDS will use a random number generation program to determine assignment.

5.4.2 Masking Procedures (if applicable)

All study staff, including investigators, study care providers, study clinician, study coordinators, and research assistants, will remain blinded to the participants' medication assignments throughout the study. Erenumab and Placebo will be packaged in identical vials and stored. Only IDS, the research pharmacy will be unblinded. If the IRB and/or Data and Safety Monitoring Board (DSMB) request an unblinded data report during the data collection period, an unblinded biostatistician will generate the report.

Unmasking/unblinding prior to study completion will occur only if there is evidence that a participant's health or safety is threatened and therefore, knowledge of treatment assignment is necessary to protect the participant.

Except in extreme medical emergencies, before a participant's treatment assignment is revealed, the investigator must confer the request for unmasking with the IDS. For a medical emergency that occurs during business hours, the site investigator will contact the IDS to determine the participant's treatment assignment; for a medical emergency that occurs outside of business hours, medical personnel will contact the IDS pharmacy to determine the treatment assignment.

An event is considered an extreme medical emergency when medical management of a participant requires the knowledge of the treatment assignment. Study participants will be provided with instructions and contact information for emergency situations. Emergency unmasking will be recorded and reported to the PI, and the medical monitor as soon as possible, with a full accounting of the event, date and time of occurrence, the reason for unmasking, and names of all individuals who were notified of the emergency. Unblinding will be reported to the Data Safety Monitoring Board (DSMB) and IRB according to the University of Maryland policies and guidelines.

